2.2.15 Drug Interactions

Drugs that inhibit or induce cytochrome P450 enzymes: Ruxolitinib is metabolized by CYP3A4 and to a lesser extent by CYP2C9.

CYP3A4 inhibitors: The C_{max} and AUC of ruxolitinib increased 33% and 91%, respectively following concomitant administration with the strong CYP3A4 inhibitor ketoconazole in healthy subjects. Concomitant administration with mild or moderate CYP3A4 inhibitors did not result in an exposure change requiring intervention. When administering Jakafi with strong CYP3A4 inhibitors, consider dose reduction.

Fluconazole: The AUC of ruxolitinib is predicted to increase by approximately 100% to 300% following concomitant administration with the combined CYP3A4 and CYP2C9 inhibitor fluconazole at doses of 100 mg to 400 mg once daily, respectively. Avoid the concomitant use of Jakafi with fluconazole doses of greater than 200 mg daily.

CYP3A4 inducers: The C_{max} and AUC of ruxolitinib decreased 32% and 61%, respectively, following concomitant administration with the strong CYP3A4 inducer rifampin in healthy subjects. No dose adjustment is recommended; however, monitor patients frequently and adjust the Jakafi dose based on safety and efficacy.

2.2.16 Over-dosage

There is no known antidote for overdoses with Jakafi. Single doses up to 200 mg have been given with acceptable acute tolerability. Higher than recommended repeat doses are associated with increased myelosuppression including leukopenia, anemia and thrombocytopenia. Appropriate supportive treatment should be given. Hemodialysis is not expected to enhance the elimination of ruxolitinib.

2.2.17 Post-marketing experience

Ruxolitinib has been granted Marketing Authorization Approval in the USA for PV not responding to hydroxyurea, intermediate or high-risk myelofibrosis, including PMF, post-polycythemia vera myelofibrosis and post-essential thrombocythemia myelofibrosis, and in Canada marketing authorization was granted in June 2012 for the

[figure not shown]
indication of splenomegaly and/or its associated symptoms in adult patients with primary myelofibrosis (also known as chronic idiopathic myelofibrosis), postpolycythemia vera myelofibrosis or post-essential thrombocythemia myelofibrosis. In the EU, the CHMP has granted a positive opinion in April 2012, and granted approval for the treatment of disease related splenomegaly or symptoms in adult patients with primary myelofibrosis (also known as chronic idiopathic myelofibrosis), post-polycythemia vera myelofibrosis, or post essential thrombocythemia myelofibrosis in August 2012. Regulatory review is ongoing in other countries. The product is currently marketed in the USA, Canada, and the European Union under the brand name JAKAFI® (USA) and JAKAVI® (Canada and EU).

3.0 PATIENT SELECTION

3.1 Eligibility

Patients with high-risk (Figure 1), previously untreated CLL/SLL that do not require therapeutic intervention according to the IWCLL guidelines, based on the Rai and Binet staging systems (Table 3), but are likely to require treatment within ≤ 4 years if remain untreated, according to the below nomogram (Figure 1) will be eligible to enroll onto the study.

Figure 1. Nomogram for time to first treatment (Wierda et al., 2011)

Nomogram used by totaling points identified at top scale for each of four independent variables. Point score for lactate dehydrogenase (LDH) identified based on *IGHV* mutation status. This summed point score then identified on total point scale to identify 2- and 4-year treatment-free probability (prob) and estimate treatment-free survival. Fluorescent in situ hybridization (FISH) was categorized by Dohner hierarchic categorization. LN, lymph node.

This nomogram provides a visual depiction of the relative contribution of each prognostic factor to the total point score and, thus, the weight of factors regarding risk for requiring first treatment. The formula for calculating the total point score is as follows: $[I(\text{No. of lymph node sites involved} = 3) \times 7.370 + I(\text{FISH} = 11q \text{ del}) \times 9.312 + I(\text{FISH} = 17p \text{ del}) \times 11.285 + (\text{diameter of largest cervical lymph node in cm}) \times 4.172 + (\text{LDH}/100) \times I([\text{IGHV gene} = \text{mutated}] \times 5.000 + (\text{LDH} \div 100) \times I([\text{IGHV gene} = \text{unmutated}] \times 1.065) + 35.467]$. The indicator function (I) is equal to 1 if the statement in the parentheses is true and is equal to 0 otherwise. The total point scores ranged from 0 to 87.4 points, with a median of 21.0.

Table 3. IWCLL recommendations for the treatment of CLL/SLL (Hallek et al., 2008)

	General practice/Clinical trial	
Treat with Rai stage 0	NGI	RQ
Treat with Binet stage A	NGI	RQ
Treat with Binet stage B or Rai stage I or Rai stage II	Possible	Possible
Treat with Binet stage C or Rai stage III or Rai stage IV	Yes	Yes
Treatment of active/progressive disease	Yes	Yes
Treat without active/progressive disease	NGI	RQ

NGI, indicates not generally indicated unless the patients shows features of disease progression or disease transformation; and RQ, research question.

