Public Description:	
BACKGROUND:
 
Disease-related symptoms impair the quality of life of patients with chronic lymphocytic leukaemia (CLL) who do not require systemic therapy. Available therapies are not specifically aimed at symptom control. Because stimulation of the B-cell receptor activates JAK2 in CLL cells and the JAK2 inhibitor ruxolitinib improves symptoms in patients with myelofibrosis, we postulated that ruxolitinib would improve disease-related symptoms in patients with CLL. We did a phase 2 trial of ruxolitinib to test this hypothesis.
 
METHODS:
 
Symptomatic patients with CLL who did not require systemic therapy were enrolled at MD Anderson Cancer Center (Houston, TX, USA) between Sept 15, 2014, and Sept 20, 2015. Participants were given 10 mg ruxolitinib orally twice a day. Scores on the Brief Fatigue Inventory (BFI), CLL module of the MD Anderson Symptom Inventory (MDASI) and symptom-associated interference in daily activities, were assessed before treatment and after 3 months. This trial is ongoing and is registered at ClinicalTrials.gov (NCT02131584).
 
FINDINGS:
 
41 patients (25 previously untreated for CLL and 16 previously treated) were enrolled. At 3 months, the mean percentage change from baseline in BFI score was 44.3% (SD 35.0, p<0.0001), in symptom interference score was 43.4% (51.5, p<0.0001), and in MDASI score was 42.1% (37.4, p<0.0001). 32 (78%) of the patients experienced 20% or greater reduction in the mean BFI, and 24 (59%) had a reduction of two units or more in worst fatigue score in past 24 hours as assessed by the BFI. The most common grade 3-4 adverse events were neutropenia (n=2 [5%]), hypertension (n=2 [5%]), insomnia (n=1 [2%]), tinnitus and dizziness (n=1 [2%]), and thrombocytopenia (n=1 [2%]).
 
INTERPRETATION:
 
In patients with CLL, ruxolitinib was associated with significant improvements in disease-related symptoms as measured by BFI, MDASI, and symptom interference scores. As of now, 60 patients have been enrolled. Analysis of these patients' outcome is pending.

Protocol Type:	Standard Protocol

Protocol Phase:	Phase II
Version Status:	Activated -- Closed to new patient entry as of 06/07/2019
Version:	11
Document Status:	Saved as "Final"
Submitted by:	[name]--9/13/2018 10:37:04 AM
OPR Action:	Accepted by: [name] -- 9/17/2018 3:40:21 PM

Which Committee will review this protocol?

- The Clinical Research Committee - (CRC)

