2.1.2 Previously untreated patients with high-risk CLL/SLL

[figure not shown]
The clinical course of patients with CLL/SLL is diverse; some patients have indolent disease, never needing treatment, whereas others have aggressive disease requiring early intervention. We currently use clinical criteria to initiate therapy. However several investigators suggested that early intervention in patients with high-risk disease might be beneficial. To determine which patients are at high risk of disease progression, a multivariable analysis was performed to identify prognostic factors independently associated with time to first treatment for patients with CLL (Wierda et al., 2011). This multivariable model was used to develop a nomogram—a weighted tool to calculate 2- and 4-year probability of treatment and estimate median time to first treatment.

The factors independently associated with shorter time to first treatment included: **a.)** three involved lymph node sites, **b.)** increased size of cervical lymph nodes, **c.)** presence of 17p deletion or 11q deletion assessed by fluorescence in situ hybridization (FISH), increased serum lactate dehydrogenase (LDH), and unmutated IgHV (Wierda et al., 2011).

Given that ruxolitinib is well tolerated and efficiently alleviates the symptoms of patients with CLL/SLL and given that, similar to ibrutinib, treatment with ruxolitinib increased and then reduced the number of circulating lymphocytes, we sought to investigate the clinical benefits of ruxolitinib in patients with previously untreated high-risk CLL/SLL. In particular, we intend to study the effect of ruxolitinib on disease burden and determine whether treatment with ruxolitinib will delay the time to next treatment of previously untreated patients with high-risk CLL/SLL who are expected to require therapy for CLL/SLL within 4 years according to the above described nomogram (Wierda et al., 2011).

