3.1.1 Inclusion criteria

- 1) Subjects who are able to understand and sign an informed consent document.
- 2) Subjects 18 years of age or older.
- 3) Subjects must be diagnosed with CLL/SLL and do not meet the IWCLL criteria for treatment (Hallek et al., 2008).
- 4) Patients should be previously untreated or have only been treated with single agent ibrutinib therapy for a period of < 3 months and were deemed ibrutinib intolerant.
- 5) Patients whose expected time to CLL/SLL treatment, according to our nomogram (Figure 1), is four years of less.
- 6) Subjects with hemoglobin values at the screening visit equal to or greater than 12.0 g/dL.
- 7) Subjects with a platelet count of at least $100 \times 10^9/L$ at the screening visit.
- 8) Subjects with an absolute neutrophil count (ANC) of equal to or higher than $0.5 \times 10^9/L$ at the screening visit.

- 9) Subject who are willing to undergo a bone marrow aspiration and biopsy and CT scan for disease burden assessment.
- 10) Patient who are capable to return to MDACC for follow-up.
- 11) Subjects with an Eastern Cooperative Oncology Group (ECOG) performance status of 0, 1 or 2.
- 12) Patient must be capable of swallowing the Ruxolotinib capsules (tablets).

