11.0 STATISTICAL CONSIDERATIONS

The study will be conducted at MDACC only. The primary endpoint will assess the clinical response (CR, PR, and a 20% reduction in tumor mass as assessed by a body scan and bone marrow aspiration/biopsy) at 6 ± 2 months after initiation of therapy.

We will incorporate an informal futility analysis when half of the total patients have reached 6 ± 2 months after initiation to assess whether the average change in the tumor mass score is less than zero (calculated as the score at enrollment minus the score at six months). If the average at this time is less than zero, the trial will be stopped early.

Because no treatment is the standard of care for these patients, we will routinely analyze the outcome of our Ruxolitinib-treated patients at a 6 \pm 2 month interval and compare their clinical outcome to that of patient who elected to receive no treatment.

Table 9 shows the probability of stopping early under several different scenarios, as well as how the overall power is for the primary analysis is affected by early stopping. The operating characteristics were produced in R version 2.13.0 by simulating 5000 trials with 17 patients at the interim and 34 patients at the end of the trial, accounting for a 15% drop out rate. The simulations stop early if the average change at 6 months is less than zero, and formally tests whether the change is not equal to zero at the final analysis using a paired *t*-test.

Table 9. Operating characteristics

True tumor burden difference (baseline score minus score at 6 months)	True SD of the Difference	Prob(Stop Early)	Power for Final Analysis
-1	2	0.9818	0.0026
0	2	0.5068	0.0218
1	2	0.0202	0.8064
2	2	0.0000	0.9998
-1	4	0.8398	0.0014
0	4	0.4958	0.0274
1	4	0.1584	0.2876
2	4	0.0198	0.8074

For primary analysis, the paired *t* test will be used to evaluate the changes of tumor burden from baseline to 6 \pm 2 months after initiation of therapy. Response rate will be estimated with 95% confidence interval. Patients who drop out early will be counted as non-responders. The Kaplan-Meier method will be used to estimate time to next treatment, and will compared to our historical data (Wierda et al., 2011) using Cox proportional hazards model, adjusting for effects of covariates. If necessary and applicable, appropriate methods such as propensity score matching will be used to match the patients of this study with the historical data to reduce comparison bias.

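### The total-point formula printed in Section 3.1 cannot produce the median score stated beside it and ranks mutated IGHV above unmutated; patients are affected only if the formula was used for criterion 5

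*Combined protocol and SAP*

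**What the plan says.** Inclusion criterion 5 (Section 3.1.1) admits "Patients whose expected time to CLL/SLL treatment, according to our nomogram (Figure 1), is four years of less". Section 3.1 gives two routes to a score.

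- **The graphic.** The Figure 1 legend says: "Nomogram used by totaling points identified at top scale for each of four independent variables". The summed points are then located on a total-point scale to read off treatment-free probability and survival. The legend adds that LDH points depend on IGHV status ("Point score for lactate dehydrogenase (LDH) identified based on" IGHV mutation status).
- **The formula.** The text continues: "The formula for calculating the total point score is as follows". The formula gives fixed points for three involved node sites, 11q deletion and 17p deletion, points per cm for the largest cervical node, and points per 100 LDH units that differ by IGHV status. It ends with + 35.467. The same paragraph closes with: "The total point scores ranged from 0 to 87.4 points, with a median of 21.0".

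Section 2.1.2 lists the factors for shorter time to first treatment and includes "increased serum lactate dehydrogenase (LDH), and unmutated IgHV".

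Section 11.0 describes the secondary analysis: "The Kaplan-Meier method will be used to estimate time to next treatment, and will compared to our historical data". The historical data come from the publication behind the nomogram.

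**The concern.** The formula stands in the eligibility section as the way to calculate the score, yet it conflicts with the summary figures in its own paragraph and with the direction of a risk factor given in Section 2.1.2. The level of the score matters as well as the ranking, because points are converted to expected time on a total-point scale.

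Criterion 5 defines the high-risk population named in both objectives. If enrolled patients were scored from the printed formula, the description of who was enrolled would be wrong to an unknown extent. The historical comparison of time to next treatment could then include patients who do not meet the criterion. If they were scored from the graphic, the fault is confined to the text.

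**Working it through.** **Inputs (formula in Section 3.1).** Three node sites 7.370; 11q deletion 9.312; 17p deletion 11.285; cervical node 4.172 per cm; LDH 5.000 per 100 units if mutated and 1.065 per 100 units if unmutated; constant 35.467 with no indicator. Indicators are 0 or 1. LDH and node diameter cannot be negative. The LDH and node values below are assumed for illustration.

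**1. Stated range and median.** With every other term at its lowest, the score is 0 + 35.467 = 35.467.
- Stated median 21.0: not attainable. The gap is 35.467 − 21.0 = 14.467.
- Stated minimum 0: not attainable, but this is weaker evidence because 0 may be the floor of a drawn scale.
- Stated maximum 87.4: attainable. For an unmutated patient with three sites, 17p deletion, LDH 500 and a 6.70 cm node: 7.370 + 11.285 + 27.952 + 5.325 + 35.467 = 87.4.

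The floor is 35.467/87.4 = 41% of the stated maximum. No assumption about LDH or patient mix is needed for the conflict with the median.

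**2. Direction of IGHV.** The other factors that Section 2.1.2 links to shorter time all add points, so more points mean higher risk. At equal LDH and other factors:

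mutated − unmutated = (5.000 − 1.065) × LDH/100 = 3.935 × LDH/100

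This is positive at every LDH above 0: +7.87 at LDH 200 (45.467 against 37.597 with no other factor) and +19.68 at LDH 500. Section 2.1.2 implies the opposite sign. Deleting the constant for everyone would remove the floor but leave this difference unchanged.

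**3. Could a lost bracket explain it?** As read from the PDF, the line has 8 opening and 7 closing parentheses. In the printed order, any bracket that ties 35.467 to an IGHV term also multiplies it by LDH/100.
- Tied to the unmutated LDH term: (1.065 + 35.467) = 36.532 points per 100 LDH. LDH 200 gives 73.064; adding three sites and 17p deletion (18.655) gives 91.719, above 87.4. LDH alone exceeds 87.4 beyond 87.4/36.532 × 100 = 239.
- Multiplied by LDH/100 for everyone: a mutated patient gets 40.467 per 100 LDH, so 80.934 at LDH 200, and exceeds 87.4 beyond LDH 216. An unmutated patient gets 73.064 at LDH 200, or 2 × (2 × 1.065 + 35.467) = 75.194 if the terms are nested. Mutated is still higher.

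The first of these does restore the IGHV direction and permits 21.0. It fails on the stated maximum, on the assumption that some unmutated patients had LDH above about 239, or about 200 with adverse nodes and cytogenetics. The documents give no LDH distribution.

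**4. One possible reading.** Suppose 35.467 is a separate term for unmutated IGHV only. At LDH 200 with no other factor, mutated scores 10.0 and unmutated 37.597. A mutated patient with no other factor reaches 21.0 at LDH 420. The order holds up to LDH 35.467/3.935 × 100 = 901. A score of 0 is approached only as LDH nears 0 (5.0 at LDH 100). This fits the median and the IGHV direction better than the printed line, but nothing in the documents confirms it.

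**The case against.** The strongest reply is that the formula may be damaged by PDF reading. The parentheses do not balance, and a coefficient appears inside an indicator. Testing bracket positions does not exclude a dropped or reordered term. This stands as a reason to check the original page first. It does not dissolve the point: losing a whole indicator is less likely than losing a bracket, and bracket placement alone does not repair the line.

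A second reply is that different LDH slopes by IGHV status are intended. That is correct, and the slopes are not criticised here. The difficulty is that, with the constant given to everyone, nothing offsets the steeper mutated slope.

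A third reply is that the formula cannot decide eligibility by itself. This stands. Criterion 5 cites Figure 1, the documents give no point cut-off, and the conversion from points to time lies in the figure. Nothing shows that any patient was scored from the formula.

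A reader might go further and infer that every mutated patient is over-scored by 35.467 points and that unmutated patients are scored correctly. That follows only from the unconfirmed reading in the last step of the working. For the same reason, the documents do not support saying that everyone scored from the formula receives a wrong score.

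**Conclusion.** The concern holds as an error in the plan as written, of minor severity. Two things follow from the documents alone: the printed formula has a floor of 35.467 against a stated median of 21.0, and it reverses the IGHV direction by 3.935 × LDH/100. The finding that re-bracketing does not help rests on the printed order of terms and, for one placement, on the LDH assumption given in the working.

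The size of the error for an individual patient cannot be stated, because the intended formula is not in the documents. The number of patients affected cannot be computed and may be zero.

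It would be tempting to conclude that ineligible patients were enrolled or that trial results are biased. The documents do not support either. They do not say which tool was applied. Nothing says that the total score enters the time-to-next-treatment model, for which Section 11.0 already plans covariate adjustment and, if needed, propensity matching. No bias in the tumour-burden change is claimed.

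**What to change.** Check the formula against the original page, Figure 1 and the source publication. Correct it so that it agrees with the stated median and with the IGHV direction in Section 2.1.2. Add one sentence saying whether the graphic or the formula was used to apply criterion 5. If it was the graphic, nothing more is needed.

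Only if the formula was used: re-score enrolled patients from screening data, and report the historical time-to-next-treatment comparison with and without any who do not meet criterion 5 on the corrected score.

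The cost is one check and one sentence. Re-scoring, if required, covers about 40 planned patients at most (34/0.85 = 40, which matches the largest sample size in Table 11). The possible downside is that some patients are reclassified as not meeting criterion 5. The protocol's version status reads "Closed to new patient entry as of 06/07/2019", so the correction serves the description of the enrolled population and that one comparison; it cannot change future enrolment.

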3.1.1 Inclusion criteria

- 1) Subjects who are able to understand and sign an informed consent document.
- 2) Subjects 18 years of age or older.
- 3) Subjects must be diagnosed with CLL/SLL and do not meet the IWCLL criteria for treatment (Hallek et al., 2008).
- 4) Patients should be previously untreated or have only been treated with single agent ibrutinib therapy for a period of < 3 months and were deemed ibrutinib intolerant.
- 5) Patients whose expected time to CLL/SLL treatment, according to our nomogram (Figure 1), is four years of less.
- 6) Subjects with hemoglobin values at the screening visit equal to or greater than 12.0 g/dL.
- 7) Subjects with a platelet count of at least $100 \times 10^9/L$ at the screening visit.
- 8) Subjects with an absolute neutrophil count (ANC) of equal to or higher than $0.5 \times 10^9/L$ at the screening visit.

- 9) Subject who are willing to undergo a bone marrow aspiration and biopsy and CT scan for disease burden assessment.
- 10) Patient who are capable to return to MDACC for follow-up.
- 11) Subjects with an Eastern Cooperative Oncology Group (ECOG) performance status of 0, 1 or 2.
- 12) Patient must be capable of swallowing the Ruxolotinib capsules (tablets).

3.1.2 Exclusion criteria

- 1) Females who are pregnant or are currently breastfeeding.
- 2) Subjects of childbearing potential who are unwilling to take appropriate precautions (Throughout the study from screening, including 30 days after discontinuation of the study drug) to avoid becoming pregnant or fathering a child.
 - Females of non-childbearing potential are defined as women who (a) are equal to or greater than 55 years of age with history of amenorrhea for 1 year, OR (b) are surgically sterile for at least 3 months.
 - For females of childbearing potential, or for males, appropriate precautions are those that are at least 99% effective in preventing the occurrence of pregnancy. These methods should be communicated to the subjects and their understanding confirmed:
 - Double barrier methods
 - Condom with spermicide in conjunction with use of an intrauterine device (IUD)
 - condom with spermicide in conjunction with use of a diaphragm
 - Oral, injectable, or implanted contraceptives
 - Tubal ligation or vasectomy (surgical sterilization)
- 3) Subjects with recent history of inadequate bone marrow reserve as demonstrated by previous transfusions except for acute blood loss (e.g. surgery) in the month prior to screening.
- 4) Subjects with inadequate liver or renal function at screening and baseline visits:
 - Alanine aminotransferase (ALT) > 2.5x ULN.
 - Modification of Diet in Renal Disease (MDRD) calculated GFR < 30 mL/min
- 5) Subjects with active uncontrolled infection or who are HIV positive (Subjects with acute infections requiring treatment should delay screening/enrollment until the course of therapy has been completed and the event is considered controlled).
- 6) Subjects with history of or a current invasive malignancy over the past 5 years except for treated ba+
- 7) sal or squamous carcinomas of the skin completely resected. Other completely resected cancers less than 5 years may be considered after PI review.
- 7) Subjects with clinically significant uncontrolled cardiac disease.
- 8) Subjects being treated concurrently with any prohibited medications, including investigational medication, rifampin, St. John's wort, and potent CYP3A4 inhibitors, Excluding ketoconazole) unless continuation of such medications are determined by the investigator to be in the best interest of the patient (as detailed in protocol section 2.2.15 and Table 3).

- 9) Subjects who have previously received JAK inhibitor therapy. ++
- 10) Subjects with active alcohol or drug addiction that would interfere with their ability to Comply with the study requirements.
- 11) Subjects with any concurrent condition that, in the Investigator's opinion, would jeopardize the safety of the subject or compliance with the protocol.
- 12) Subjects who have unknown transfusion history.
- 13) Patients who cannot comply with the study requirements.

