2.2.4 Drug Interactions

Strong CYP3A4 inhibitors: In a trial of 16 healthy volunteers, a single dose of 10 mg of Jakafi was administered alone on Day 1 and a single dose of 10 mg of Jakafi was administered on Day 5 in combination with 200 mg of ketoconazole (a strong CYP3A4 inhibitor, given twice daily on Days 2 to 5). Ketoconazole increased ruxolitinib C_{max} and AUC by 33% and 91%, respectively. Ketoconazole also prolonged ruxolitinib half-life from 3.7 to 6.0 hours.

Fluconazole: Simulations using physiologically-based pharmacokinetic (PBPK) models suggested that fluconazole (a dual CYP3A4 and CYP2C9 inhibitor) increases steady state ruxolitinib AUC by approximately 100% to 300% following concomitant administration of 10 mg of Jakafi twice daily with 100 mg to 400 mg of fluconazole once daily, respectively.

Mild or moderate CYP3A4 inhibitors: In a trial of 15 healthy volunteers, a single dose of 10 mg of Jakafi was administered alone on Day 1 and a single dose of 10 mg of Jakafi was administered on Day 5 in combination with 500 mg of erythromycin (a moderate CYP3A4 inhibitor, given twice daily on Days 2 to 5). Erythromycin increased ruxolitinib C_{max} and AUC by 8% and 27%, respectively.

CYP3A4 inducers: In a trial of 12 healthy volunteers, a single dose of 50 mg of Jakafi was administered alone on Day 1 and a single dose of 50 mg of Jakafi was administered on Day 13 in combination with 600 mg of rifampin (a strong CYP3A4 inducer, given once daily on Days 3 to 13). Rifampin decreased ruxolitinib C_{max} and AUC by 32% and 61%, respectively. In addition, the relative exposure to ruxolitinib active metabolites increased approximately 100%.

In vitro studies: *In vitro*, ruxolitinib and its M18 metabolite do not inhibit CYP1A2, CYP2B6, CYP2C8, CYP2C9, CYP2C19, CYP2D6 or CYP3A4. Ruxolitinib is not an inducer of CYP1A2, CYP2B6 or CYP3A4 at clinically relevant concentrations. *In vitro*, ruxolitinib and its M18 metabolite do not inhibit the P-gp, BCRP, OATP1B1, OATP1B3, OCT1, OCT2, OAT1 or OAT3 transport systems at clinically relevant concentrations. Ruxolitinib is not a substrate for the P-gp transporter.

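### Exclusion 8's investigator override, as worded, reaches concurrent investigational medication in a single-arm response trial; Table 5 also needs a CLL/SLL starting-dose line

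*Combined protocol and SAP*

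**What the plan says.** **The override.** Exclusion 8 in Section 3.1.2 lists investigational medication, rifampin, St. John's wort and potent CYP3A4 inhibitors together as prohibited. Ketoconazole appears to be exempted, although the bracket around that phrase is unmatched. The exclusion then applies "unless continuation of such medications are determined by the investigator to be in the best interest of the patient", followed by the reference "as detailed in protocol section 2.2.15 and Table 3".

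**What the reference leads to.** Section 2.2.15 covers CYP3A4 inhibitors ("When administering Jakafi with strong CYP3A4 inhibitors, consider dose reduction"), fluconazole ("Avoid the concomitant use of Jakafi with fluconazole doses of greater than 200 mg daily") and CYP3A4 inducers. It does not mention investigational drugs. The other target is headed "Table 3. IWCLL recommendations for the treatment of CLL/SLL" and has nothing to do with interactions.

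**Entry criteria that narrow the problem.** Inclusion 4 reads "Patients should be previously untreated or have only been treated with single agent ibrutinib therapy for a period of < 3 months", with ibrutinib intolerance also required for the treated patients. Exclusion 6 removes "Subjects with history of or a current invasive malignancy over the past 5 years", with exceptions for certain resected cancers.

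**Data capture.** Section 12.0 leaves concomitant medications in the electronic medical record and does not require them in the trial's data capture.

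**Dosing with interacting drugs.** Section 5.1 requires a dose change with strong CYP3A4 inhibitors or with fluconazole up to 200 mg, and Table 5 supplies the doses. Its starting rows are labelled for myelofibrosis and polycythemia vera. Its rows for all patients apply only once a dose is stable. Section 4.1 sets CLL/SLL starts of 20, 15 or 10 mg bid without mentioning interacting drugs.

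**The concern.** The primary analysis in Section 11.0 is a within-patient change in tumour burden at 6 ± 2 months, with a response rate alongside. There is no randomised control. The untreated and historical comparisons that the section mentions would not remove the effect of a second agent taken only by treated patients. A rule that lets an investigator keep a patient on another investigational drug therefore admits a confounder that this design cannot adjust for. Because such use need not reach the analysis dataset, the analyst might not know whom to set aside.

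The dosing point is separate and smaller. A CLL/SLL patient who begins ruxolitinib while taking an interacting drug has no Table 5 row that applies by its label. Most readers would halve the dose. Someone who borrowed the myelofibrosis row would give 10 mg bid to everyone, including patients whose start had already been lowered to 10 mg bid for hemoglobin of 12-13 g/dL. For them the interaction would not be offset, on a drug known to cause anemia.

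**Working it through.** **Part 1: scope of the override.** No arithmetic applies, so the texts are read against each other.

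1. Investigational medication is one of the named items in exclusion 8. The waiver clause refers back to the drugs just listed and carves none of them out.
2. The bracketed reference is the only possible limit. Section 2.2.15 is silent on investigational drugs: it neither sets a condition for their use nor says the waiver excludes them. Table 3 is the wrong table. Neither expressly narrows the clause.
3. No other section of the documents supplied bars concurrent investigational drugs.
4. Inclusion 4 blocks most patients on an investigational CLL drug, and exclusion 6 blocks most patients treated for another recent cancer. What remains is mainly an investigational agent for a non-cancer condition.
5. The documents give no basis for how often that would occur or how far it would move tumour response, so no figure is offered.

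**Part 2: starting dose with an interacting drug.** Inputs: the Section 4.1 starts; Table 5's myelofibrosis row for platelets of at least 100 × 10⁹/L (10 mg bid); Table 5's stable-dose rule (halve and round up to tablet strength); Section 2.2.7, which advises a cut of about 50% with strong CYP3A4 inhibitors; and the 5 mg clinical supply tablet (Section 6.0).

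| Section 4.1 start | Halved, rounded up | Myelofibrosis row, if borrowed |
|---|---|---|
| 20 mg bid | 20 × 0.5 = 10 mg bid | 10 mg bid |
| 15 mg bid | 15 × 0.5 = 7.5, up to 10 mg bid | 10 mg bid |
| 10 mg bid (hemoglobin 12-13 g/dL) | 10 × 0.5 = 5 mg bid | 10 mg bid (no cut) |

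The two readings differ only in the last row, by 10/5 = 2.0-fold.

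**Exposure for that group.** Section 2.2.7 states linear pharmacokinetics from 5 to 200 mg, so the bid-equivalent dose is the dose times the AUC ratio.

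- Ketoconazole: Section 2.2.4 gives AUC +91%, a ratio of 1.91. Uncut: 10 × 1.91 = 19.1 mg. Halved: 5 × 1.91 = 9.55 mg.
- Fluconazole 100 mg: Section 2.2.4 reports simulations in which the drug "increases steady state ruxolitinib AUC by approximately 100% to 300% following concomitant administration of 10 mg of Jakafi twice daily" over fluconazole 100 to 400 mg daily. At 100 mg the ratio is 2.0. Uncut: 10 × 2.0 = 20.0 mg. Halved: 5 × 2.0 = 10.0 mg.

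Uncut, these patients have 1.91 to 2.0 times the exposure Section 4.1 assigned them, close to the 20 mg bid top start. Halved, they have 0.96 to 1.0 times.

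**The case against.** **On the override.** The reference to Section 2.2.15 can be read as confining the waiver to interacting drugs, and that may well be what was meant. The waiver covers only continuation, so it concerns drugs already being taken at entry. Inclusion 4 and exclusion 6 remove most relevant agents, exclusion 9 removes prior JAK inhibitors, and exclusion 11 leaves room to refuse an unsafe combination. On this view, only a drafting preference remains. The rarity stands, and so does the absence of any size. The limit itself does not: the exclusion names investigational medication, the waiver does not except it, and half of the reference is to the wrong table. A reader might also infer that such drugs were used, or that the response estimate is biased. Nothing in the documents supports either inference.

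**On the dosing gap.** Most of the objection stands. The myelofibrosis row by its own heading does not apply to CLL/SLL. Borrowing it would leave the hemoglobin 12-13 g/dL group unmodified, contrary to Section 5.1. Section 2.2.7 already gives a cut of about 50% for strong CYP3A4 inhibitors, not tied to a disease or to a stable dose. It gives no rule for fluconazole, but Section 5.1 and the stable-dose row treat the two alike. Exclusion 5 (HIV infection, and acute infections still under treatment) removes many likely users of the drugs named in Section 5.1. CBCs every 2-4 weeks (Section 4.4) and the required adjustment for falling hemoglobin (Section 4.1) limit the harm.

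**On exceeding 25 mg bid.** A reader might interpolate to fluconazole 200 mg and conclude that the Section 2.2.13 maximum is passed. Linear in dose, the increase is 100% + (100/300) × 200% = 167%, and 10 × 2.67 = 26.7 mg. On log dose it is 200%, and 10 × 3.0 = 30.0 mg. The documents do not support that conclusion. They give no figure at 200 mg, and the 25 mg limit is an administered dose, whereas these are exposure equivalents. The same values would also hold for 20 and 15 mg starters correctly cut to 10 mg bid, so they do not come from the missing row.

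**Conclusion.** The concern holds in limited form and is minor. Its main part is the override: as written it lets an investigator continue another investigational drug in a trial that has no means of separating that drug's effect and no requirement to record it in the analysis data. This rests on the plain wording of exclusion 8 and on the absence of a limiting statement elsewhere in the documents supplied. Use is expected to be uncommon, and no size of bias is claimed.

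The missing CLL/SLL row is a secondary clarification. It affects only hemoglobin 12-13 g/dL starters who also take an interacting drug, and only if the dose is left uncut. The documented consequence is 19.1 to 20.0 mg bid-equivalent against the 10 mg bid assigned, assuming the stated linear pharmacokinetics and, for fluconazole 100 mg, the simulated increase. No claim is made that the 25 mg maximum is exceeded. The Table 3 reference is a clerical slip. Sample size, power and error rates are unaffected.

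**What to change.** 1. Make concurrent investigational medication an absolute exclusion, and keep the investigator override only for rifampin, St. John's wort and potent CYP3A4 inhibitors.
2. Add a CLL/SLL starting line to Table 5: with a strong CYP3A4 inhibitor or fluconazole up to 200 mg daily, begin at 50% of the Section 4.1 dose, rounded up to tablet strength (20 to 10, 15 to 10, 10 to 5 mg bid). This agrees with Section 2.2.7 and the stable-dose rule, uses the 5 mg tablet, and lands on levels already in Table 4.
3. Editorial: in exclusion 8, replace Table 3 with Section 5.1/Table 5.

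The cost is the wording of one criterion, one table row and one cross-reference, with at most a few screened patients lost. The version is marked closed to new entry, so for patients already enrolled the practical step is a check of the medical records: was the override used for an investigational drug, and did anyone start uncut on an interacting drug? Any such cases should be reported with the results.
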